#### SCHEMA

#### Patient Eligibility:

- Histological or cytological evidence of small cell lung cancer (SCLC)
- Zubrod performance status of  $\leq 1$
- RTOG neurological function class of 1 or 2 (Appendix A)
- Limited disease with CR to chemotherapy and consolidative chest radiotherapy that was documented at least on standard chest X-rays within one month of study entry.
- No definitive evidence of brain metastases on brain MRI or CT scan at least one month before protocol entry.

[figure not shown]
#### **Treatment Plan:**

Patients with limited stage SCLC s/p chemotherapy and thoracic radiation

[figure not shown]

#### 1. OBJECTIVES

#### 1.1 Primary Objectives

Evaluate performance on the Hopkins Verbal Learning Test-Revised for delayed recall (HVLT-R-delayed recall) at 6 months following hippocampal-sparing PCI relative to a historical control receiving standard PCI.

#### **1.2** Secondary Objectives

- 1.2.1 Evaluate performance on HVLT-R delayed recall at 12 months following hippocampal-sparing PCI relative to historical control receiving standard PCI.
- 1.2.2 Evaluate composite cognitive function at 6 and 12 months following hippocampal-sparing PCI relative to a historical control receiving standard PCI
- 1.2.3 Evaluate quality of life following hippocampal-sparing PCI relative to a historical control receiving standard PCI.
- 1.2.4 Determine whether development of brain metastases following hippocampalsparing PCI is higher than expected.
- 1.2.5 Determine whether development of leptomeningeal carcinomatosis following hippocampal sparing PCI is higher than expected
- 1.2.6 Evaluate overall survival following hippocampal sparing PCI.

#### 2. BACKGROUND

#### 2.1 Study Disease and Rationale

The current standard of care for treatment of limited stage small cell lung cancer consists of chemotherapy plus thoracic irradiation (1), followed by prophylactic cranial irradiation (PCI). The recommendation for PCI is based on the results of a meta-analysis in patients with limited stage small cell lung cancer which demonstrated a 5.4% increase in overall survival with the addition of PCI to chemo-radiation therapy for the primary lung tumor (2).

Unfortunately, it is well documented that whole brain radiation therapy is associated with neurocognitive toxicity (3-7) and that there is a direct relationship between neurocognitive dysnfunction and worsening quality of life (8). This toxicity is particularly important in patients being treated with PCI for SCLC since they represent a potentially curable patient population who have a relatively high likelihood of surviving long enough to develop the long-term sequalae of therapy.

The precise mechanism of radiation induced neurotoxicity remains unclear and the effect is likely multi-factorial. However, emerging data suggests that radiation induced damage to neural progenitor cells within the hippocampus may play a role. Animal studies have shown that new neurons and glia are produced throughout adult life from neural stem cell precursors in the subventricular zone of the lateral ventricles and the subgranular zone of the hippocampal dentate gyrus (9-11). These cells play an important role in injury repair within the central nervous system (12,13). Similarly, these cells migrate to the site of inflammation caused by irradiation or brain injury (13).

Multiple animal studies have shown that neural progenitor cells are extremely sensitive to radiation (14-17). Tada et al. showed that 2 Gy of radiation effectively killed proliferating cells in both the SVZ of the lateral ventricles (14) and the subgranular zone of the dentate gyrus (15). The anti-proliferative effects last for up to 15 months after a single radiation treatment (18) and are dose dependent (19,20). There is repair over time following low doses of radiation, suggesting likely recovery of cells with fractionation (14).

There is an association between radiation-induced neural progenitor cell impairment and neurocognitive decline after central nervous system irradiation in rodents. Cranial irradiation significantly decreases hippocampal neurogenesis and is associated with impaired performance of hippocampal-dependent tasks 19-22, indicating that newly born cells may be essential for normal hippocampal functioning.

Several studies suggest that neurogenic areas similar to those described in the rodent brain exist in the human brain as well. For example, Eriksson et al. (23) demonstrated that progenitor cells in the human dentate gyrus divide to form new neurons, while Sanai et al. (24) found that astrocytes in the human SVZ of the lateral ventricles divide in vivo and act as multipotent progenitor cells in vitro. Human studies have likewise demonstrated cognitive deficits following cranial irradiation, most notably in children (25-28). This decline includes diminished capability to learn and memorize new tasks and information, as well as a dramatic reduction in full-scale IQ (29).

Recent human studies have demonstrated that it is possible to use intensity modulated radiation therapy (IMRT) to reduce the radiation dose to the hippocampus during radiation therapy for brain tumors (30-32). In addition, preliminary data using a mouse model has suggested that NPC sparing radiation may allow improved survival of neural progenitor cells compared to conventional radiation treatment plans, at least at an early time point (33). Similarly, recent data from a prospective study in children treated with radiation therapy to the brain suggests an inverse relationship between radiation dose to the hippocampus and performance on neurocognitive testing (34), and a randomized trial comparing 25 Gy versus 36 Gy of PCI found that the risk of chronic neurotoxicity was significantly higher in the 36 Gy arm (35).

The purpose of this study is to evaluate performance on neurocognitive testing following hippocampal-sparing PCI relative to the historical experience of patients (RTOG 0212) who received standard PCI.

#### 2.2 Correlative Studies Background

Correlative studies include a neurocognitive function test battery that has been validated in a multi-institutional phase III study by the Radiation Therapy Oncology Group (RTOG) in the context of brain metastases (36,37). The tests will be performed by a trained examiner. The tests utilized in this protocol are described briefly below:

#### 2.2.1 Mini Mental State Examination

The Mini Mental State Examination (38) is designed to evaluate global function. It consists of six tasks designed to evaluate short-term memory retention and recall, attention, and language. The maximum score is 30. Scores fall into 4 categories:

- 24-30: "Normal" range
- 20-23: Mild cognitive impairment
- 10-19: Moderate cognitive impairment
- 0-9: Severe cognitive impairment

#### 2.2.2 Trail Making Test

The Trail Making Test A is designed to evaluate visual motor scanning speed and the Trail Making Test B is designed to evaluate executive function (39,40). These tests require patients to connect circles in numerical (part A) or alternating numerical and alphabetical sequence (part B) within a timed interval of less than 5 minutes for each test. Results are reported as the number of seconds required to complete the task with higher scores reflecting higher degrees of impairment.

	Average	Deficient	Rule of Thumb
Trail A	29 seconds	>78 seconds	Most in 90 seconds
Trail B	75 seconds	>273 seconds	Most in 3 minutes

#### 2.2.3 Controlled Oral Word Association Test

The Controlled Oral Word Association Test (COWAT) is designed to evaluate letter-cued verbal fluency. It requires patients to name words beginning with a specific letter with increasing associated activity, in three 1minute periods.

Scoring is based on the number of words named during the 1minute periods, with adjustments for education and age. Individual scores are categorized as intact, low average, borderline, deficient, or seriously deficient, based on their scores after these adjustments (41).

#### 2.2.4 Hopkins Verbal Learning Test-Revised

The Hopkins Verbal Learning Test-Revised is designed to evaluate memory. It requires patients to memorize a list of 12 items for three consecutive tests (recall), to identify the same 12 items from a list of semantically related or unrelated items (recognition), and to recall the same 12 items after a 15minute delay (delayed recall). Scoring and interpretation are simple, and outlined in a professional manual (42).

### 2.2.5 EORTC Quality of Life questionnaire (QLQ-C30) and the Brain Cancer Module 20

The EORTC Quality of Life questionnaire (QLQ-C30, Appendix B) is a 30 item questionnaire designed for and validated in cancer patients. It consists of 9 multi-item scales—1 global scale, 5 functional scales (physical, role, emotional, cognitive and social), 3 symptom scales (nausea, pain, fatigue). The remaining 6 questions are single items addressing other symptoms and financial impact. The Brain Cancer Module 20 (BN 20, Appendix C) is a 20 question addendum to QLQ-C30 designed specifically for patients with brain tumors. It assesses neurologic deficits, future uncertainty and disease and treatment related symptoms.

#### 2.3 Additional Testing

The following tests will be administered to the subject after those outlined in Section 2.2 have been completed.

#### 2.3.1 Brief Visuospatial Memory Test-Revised

The Brief Visuospatial Memory Test-Revised is designed to evaluate nonverbal/visuospatial learning and memory. It serves as a non-verbal analogue to the HVLT-R, and is generally more sensitive to right hippocampal functioning. It requires patients to learn a series of six figures printed on a page over the course of three exposure trials (immediate recall), recall those same six figures after a 15-20 minute delay (delayed recall), and identify the figures from among an equal number of foils (recognition). Scoring and interpretation are simple, and outlined in a professional manual (43).

#### 2.3.2 Category-cued verbal fluency

The Category Fluency Test is designed to evaluate semantically-guided verbal generativity and is often administered in conjunction with the COWAT. It requires patients to name as many different category exemplars as they can in 2 60-second trials. Scoring involves tallying the number of acceptable words reported for the two trials and interpretation is simple and outlined in a professional manual (44).

#### 2.3.3 Brief Test of Attention

The Brief Test of Attention is designed to evaluate auditory divided attention and can be used with individuals with visual and motor impairments that preclude tests requiring visual scanning or manual dexterity. It requires patients to count numbers or letters from lists read aloud consisting of both types of stimuli. The number of correctly monitored lists is tallied, with raw scores ranging from 0 to 20. Interpretation is simple and outlined in a professional manual (45).

#### 2.3.4 Hopkins Adult Reading Test

The Hopkins Adult Reading Test is designed to evaluate pre-illness intellect. It requires patients read aloud a series of 35 printed, phonetically irregular words. The number of correctly pronounced words is tallied and entered into a formula along with demographic characteristics to estimate WAIS-III Full Scale IQ [(86.664 + 0.145(age) - 6.136(sex) - 8.642(race) + 0.564(educ) + 0.862 + 1.140(HART), when age is coded in years; sex is coded 1 (male) or 2 (female); race is coded 1 (non-black) or 2 (black); education is coded in years as the highest grade completed] (46).

#### 2.3.5 Perceptual Comparison Test

The Perceptual Comparison Test is designed to evaluate mental processing speed. It requires patients make speeded same/different distinctions in response to pairs of letter strings and pairs of patterns over the course of two 90-second trials. Scoring involves tallying the number of correct responses across the two trials, with higher scores reflecting faster processing speed (47).

#### **3. PATIENT SELECTION**

#### 3.1 Eligibility Criteria

**3.1.1** Histologic proof or unequivocal cytologic proof (fine needle aspiration, biopsy, or two positive sputa) of SCLC

- **3.1.2** Patients must have limited disease SCLC after clinical staging evaluation: clinical TNM stages I-IIIB (i.e., confined to one hemithorax, but excluding T4 tumor based on malignant pleural effusion and N3 disease based on contralateral hilar or contralateral supraclavicular involvement) according to AJCC 1997 staging manual to be consistent with RTOG 0212
- **3.1.3** Patients must have completed all of their prescribed chemotherapy at least one week prior to study entry; the plan for PCI should be such that PCI begins no more than 240 days from the start of induction chemotherapy
- **3.1.4** Patients must have achieved a complete response to induction chemotherapy (+/-thoracic radiation therapy) assessed according to local habits (at least on a chest xray) at the time of study entry.

**3.1.5** Patients may have started consolidative chest irradiation by the time of study entry.

- **3.1.6** Age  $\geq$  18 years.
- **3.1.7** Zubrod performance status  $\leq 1$

**3.1.8** No definitive evidence of brain metastases on brain CT scan or brain MRI < 1 month prior to study entry

- **3.1.9** Neurological function class of 0-2 (Appendix A)
- **3.1.10** Patients of childbearing potential (male or female) must practice adequate contraception due to possible harmful effects of radiation and chemotherapy on an unborn child.

**3.1.11** Neuropsychological tests will be performed by a trained examiner.

**3.1.12** Long-term follow up must be possible.

3.1.13 Patients must sign a study-specific informed consent prior to study entry.

**3.1.14** All patients must be informed of the investigational nature of this study and must be given written informed consent in accordance with institutional and federal guidelines.

**3.1.15** If a woman is of child-bearing potential, a negative urine or serum pregnancy test must be demonstrated prior to treatment. Women of childbearing potential and men must agree to use adequate contraception (hormonal or barrier method of birth control; abstinence) for the duration of study participation and for up to 12 weeks following the study. Should a women become pregnant or suspect she is pregnant while participating in this study she should inform her treating physician immediately.

#### 3.2 Exclusion Criteria

**3.2.1** Patients receiving prior external beam irradiation to the head or neck, including any form of stereotactic irradiation

**3.2.2** Radiographic evidence of brain metastases and/or ipsilateral lung metastases/malignant pleural effusion

3.2.3 Planned concurrent chemotherapy or antitumoral agent during PCI

**3.2.4** Concomitant malignancy or malignancy within the past five years other than nonmelanomatous skin cancer or carcinoma *in situ* of the cervix

**3.2.5** Patients with minimal pleural effusion evident on CXR; minimal pleural effusion visible on chest CT is allowed.

3.2.6 Patients with epilepsy requiring permanent oral medication

**3.2.7** Patients must not have a serious medical or psychiatric illness that would, in the opinion of the investigator, prevent informed consent or completion of protocol treatment, and/or follow-up visits.

**3.2.8** Patients may not take Memantine. This is the only eligibility criterion that has been added to those of RTOG 0212, since some physicians might now prescribe Memantine. This medication would not have been given at the time of enrollment on RTOG 0212 and its administration could confound the results of this study.

#### 3.3 Inclusion of Women and Minorities

Both men and women and members of all races and ethnic groups are eligible for this trial.

#### 4. **REGISTRATION PROCEDURES**

Patients will be accrued from Johns Hopkins Medical Institutes. Contact information for the Principal Investigator is listed on the cover page.

To register the patient, the following documents must be completed and faxed or e-mailed to the Study Coordinator:

- Copy of operative note and pathology report
- Source documentation verifying eligibility
- Eligibility checklist
- Signed patient consent form
- HIPAA authorization form

If the patient is deemed eligible for the study, the Study Coordinator will register the patient and assign a study number

#### 5. TREATMENT PLAN

#### 5.1 Radiation

#### 5.1.1 Radiation Simulation and Prescription

Patients will be treated to a total dose of 25 Gy with a once daily fractionation schedule of 2.5 Gy per fraction, administered five days per week. All patients will undergo CT simulation. They will be treated in a supine position using an aquaplast mask system for immobilization.

#### 5.1.2 Hippocampal sparing

The hippocampus will be defined according to the RTOG atlas. It will be contoured on the simulation CT scan using a coregistered MRI as a reference. A treatment plan will be generated in which the mean radiation dose to the true hippocampus avoidance region is < 8 Gy

#### 5.1.3 Equipment, Radiation Technique, and Dosimetry

Patients will be treated using a megavoltage linear accelerator with nominal beam energy of 6 MV. At least 90% of the whole brain should receive 90% of the prescription dose.

#### 5.1.4 Beam Verification

Either on-line cone beam CT guidance or weekly portal imaging will be used for precise patient setup.

#### 5.1.5 Therapy Interruption

For radiation therapy interruptions of up to and including 14 days, irradiation should be completed to the full prescribed dose. On the last day, the total number of fractions and the reasons for interrupting therapy must be documented

If radiation therapy interruption goes beyond 14 days, the patient will be removed from the protocol treatment. Resumption and completion of treatment will then be at the discretion of the radiation oncologist in consultation with the principal investigator. All patients who initiate protocol treatment will be followed per the study calendar.

#### 5.1.6 Risks of Radiation

Short term toxicities of radiation therapy include fatigue, alopecia, erythema or irritation of the skin, dry skin, headaches, worsening of current symptoms, edema of brain requiring steroids, ear pain or discomfort, damage to the baby if patient is or becomes pregnant, seizures, neurologic deficits depending on tumor location, edema of brain requiring surgery, death. Long term toxicities include memory loss, cataracts, edema of the brain requiring steroids, vision loss, hearing loss, necrosis of brain requiring surgery second tumor or cancer caused by radiation.

#### 5.2 Duration of Follow Up

Patients will be followed until death or the time of data analysis. Follow-up visits may be performed at outside hospitals and records sent to Johns Hopkins. Patients will undergo neurocognitive and QOL testing at baseline and 6 months and 12 months following PCI. They will have brain MRI every six months for 2 years following completion of PCI. It is preferred that MRIs be performed at Johns Hopkins Hospital but they may also be performed at outside facilities as necessary for insurance, scheduling, or other reasons.

#### 5.3 Criteria for Removal from Study

Patients will be removed from the study for the following reasons:

- 5.3.1 Unacceptable toxicity from therapy. Toxicity must be appropriately documented.
- 5.3.2 Development of intercurrent, non-cancer related illness that prevents either continuation of therapy or regular follow-up.
- 5.3.3 The patient may decide to discontinue enrollment in the protocol at any time and for any reason.

All reasons for discontinuation of treatment must be documented.

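### Section 5.3 takes patients who stop PCI for toxicity or illness out of the study, while 5.1.5 and 5.2 keep following them; reconcile the wording so that their 6-month memory scores are kept

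*Combined protocol and SAP*

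**What the plan says.** Section 5.3 (Criteria for Removal from Study) begins "Patients will be removed from the study for the following reasons". Item 5.3.1 reads "Unacceptable toxicity from therapy. Toxicity must be appropriately documented". Item 5.3.2 covers intercurrent, non-cancer "illness that prevents either continuation of therapy or regular follow-up". Item 5.3.3 is the patient's own decision to leave. The section then closes with "All reasons for discontinuation of treatment must be documented", which speaks of treatment and not of the study. It makes no exception for outcome testing and has no cross-reference to other sections.

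Section 5.1.5 (Therapy Interruption) does separate the two ideas. After an interruption of more than 14 days, "the patient will be removed from the protocol treatment", and the paragraph ends "All patients who initiate protocol treatment will be followed per the study calendar". Section 5.2 adds "Patients will be followed until death or the time of data analysis" and schedules cognitive testing at baseline, 6 months and 12 months.

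The primary endpoint (8.1.2, 8.4) is the change in HVLT-R delayed recall from baseline to 6 months. Section 8.2.1 tests it one-sided at 5% against a mean decline of 1, with 100 evaluable patients out of 125 enrolled. Neither 8.2.1 nor 8.4 says how patients who stopped treatment early are handled, beyond the allowance of 20% not evaluable.

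**The concern.** Leaving treatment and leaving the study are different events, and 5.3 does not separate them. A site that follows 5.3 literally would not bring a patient who stopped PCI for toxicity back for the month-6 test. A site that follows 5.1.5 and 5.2 would.

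What is at stake is selective loss of the primary endpoint. There is no concurrent control arm to share the loss; the remaining patients' mean is compared with a fixed number. The risks in 5.1.6 include seizures and neurologic deficits in the short term, and "Long term toxicities include memory loss" is also stated there, so the reason for removal may be related to memory. If those removed decline more than average, the analysed mean looks better than the truth and H0 is rejected too often. If they decline by the average there is no bias, and if they decline less the bias runs the other way.

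**Working it through.** **The conflict, case by case, for a patient who has started PCI**

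| Situation | Section 5.3 | Sections 5.1.5 and 5.2 |
|---|---|---|
| Stops for unacceptable toxicity | Out of the study (5.3.1) | Followed per calendar |
| Stops because illness prevents therapy | Out of the study (5.3.2, first part) | Followed per calendar |
| Illness prevents regular follow-up | Out of the study (5.3.2, second part) | Score may be unobtainable in any case |
| Patient withdraws | Out of the study (5.3.3) | Score may be unobtainable in any case |

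Only the first two rows are at issue.

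**The plan's own figures (8.2.1)**

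Inputs: difference 1 − 0.12 = 0.88, SD 3, n = 100, one-sided 5%.

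- SE = 3/√100 = 0.3.
- Power = Φ(0.88/0.3 − 1.645) = Φ(1.288) = 0.901, against 90% stated.
- Enrolment = 100/(1 − 0.20) = 125, as stated.

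**Power if removals come on top of the 25 allowed losses (assumption)**

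The same formula gives 88.8% with 5 further losses (n = 95) and 87.2% with 10 (n = 90). Loss of power is a minor matter.

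**Bias from selective loss (illustration)**

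Let f be the share removed, L their mean decline and μ the true mean decline in all patients. The documents give neither f nor L, so both are assumed. The number analysed is held at 100 and the SD at 3.

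- Mean among those left: m = (μ − fL)/(1 − f).
- H0 is rejected when the observed mean is below 1 − 1.645 × 0.3 = 0.5065.
- P(reject) = Φ((0.5065 − m)/0.3).

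| μ | f | L | m | P(reject) |
|---|---|---|---|---|
| 1.00 | 0 | – | 1.000 | 0.050 |
| 1.00 | 2% | 3 | 0.959 | 0.066 |
| 1.00 | 5% | 3 | 0.895 | 0.098 |
| 1.00 | 5% | 1 | 1.000 | 0.050 |
| 1.00 | 5% | 0 | 1.053 | 0.034 |
| 1.13 | 0 | – | 1.130 | 0.019 |
| 1.13 | 5% | 3 | 1.032 | 0.040 |

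The value 1.13 is the RTOG 0212 decline quoted in 8.2.1.

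At f = 5% and L = 3 the shift is 1 − 0.895 = 0.105 points, and 0.105/0.88 = 12% of the difference the trial is powered for.

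An error of 0.10 requires m = 0.891. With 2% removed, that means L = (1 − 0.891 × 0.98)/0.02 = 6.3 points on a 0–12 scale.

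**Check with the planned test**

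A simulated one-sided Wilcoxon signed-rank test of (change − 1), with n = 100, normal changes, SD 3 and 20,000 runs, gives 0.050 with no removal, 0.066 for 2% with L = 3, and 0.095 for 5% with L = 3. With changes rounded to whole numbers the figures are 0.049, 0.063 and 0.093.

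**The case against.** The strongest reply is that the protocol already settles the matter. Section 5.1.5 follows everyone who starts PCI, 5.2 follows patients to death or analysis, 8.4 says each patient is assessed before and after therapy, and the last line of 5.3 itself speaks of treatment. Harm requires someone to read one section literally against the others. This stands as a statement of probable intent. But the 5.1.5 sentence sits under a heading on interruptions, and 5.3 is where a coordinator would look for the removal rule.

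The link to memory can also be questioned. Memory loss is listed as a long-term toxicity, so it is an unlikely reason to stop a ten-fraction course. The calendar has no scheduled visit between week 2 and month 6, and late toxicity first found at month 6 would not by itself prevent that visit's test. This stands and keeps the exposure small.

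The direction of bias is not certain either. Section 2.1 describes radiation effects as dose dependent and reports more chronic neurotoxicity at 36 Gy than at 25 Gy. Patients who stop early receive less dose and might decline less, in which case losing them is conservative (0.034 in the table). This also stands.

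Finally, a rule in 8.4 on who is analysed could be called a separate choice of estimand. That carries less weight. Section 8.4 does not exclude patients who did not complete treatment, so the added sentence makes its present wording explicit. The 20% allowance does not answer the point: it protects the number of patients, not their representativeness.

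**Conclusion.** The concern holds. Section 5.3 conflicts with 5.1.5 and 5.2 for patients who start PCI and stop because of toxicity or illness, and 5.3 applied as written can lose their primary-endpoint scores. The conclusion rests on the text; the figures only show that a few selectively lost scores could matter.

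The size is uncertain and probably small. Of the cases computed with H0 true, the most adverse (5% removed, mean decline 3) roughly doubles the one-sided error. At 2% the effect is modest, and the bias disappears or reverses if those removed decline by the average or less. If the true decline is 1.13, the rejection rate stays below 0.05 even in that 5% case. The wording should be corrected because the contradiction touches the primary endpoint and costs almost nothing to remove. Confidence is medium, since the documents do not say how many patients would be affected.

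**What to change.** 1. In 5.3, reword so that 5.3.1 and the therapy part of 5.3.2 refer to removal from protocol treatment, in line with 5.1.5 and 5.2. Leave 5.3.3 and the follow-up part of 5.3.2 as they are.
2. State in 5.3 that every patient who starts PCI remains in the scheduled assessments unless consent is withdrawn or the patient cannot be tested.
3. Add one sentence to 8.4: the primary analysis includes every patient with a baseline and a 6-month HVLT-R delayed recall score, whether or not PCI was completed.

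The rules on when treatment stops are not touched. The cost is a wording amendment. The assessments are already in the study calendar, and the targets of 100 evaluable and 125 enrolled are unchanged. Scores from patients too ill to be tested will still be missing; the change does not recover those.
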